5.2.2.3. Geometric Mean Fold Rises

The GMFRs will be calculated as the mean of the difference of logarithmically-transformed assay results (later minus earlier) and exponentiating back to the original units. The associated 2-sided 95% CIs will be computed by exponentiating the CIs using Student's t-distribution for the mean difference on the natural log scale.

CCI

[figure not shown]

5.3. Methods to Manage Missing Data

A partial AE start date (missing day, missing both month and day) will be imputed by assigning the earliest possible start date using all available information, such as the stop date of the AE and the vaccination date(s) from the same participant, following the Pfizer standard of handling incomplete AE start date. A complete missing start date for an AE is not allowed in the data collection. No additional imputation will be applied unless stated otherwise (see [Section 3](#)).

The LLOQ for each assay will be provided by Vaccine Research & Development as part of the electronic data transfer or within the Clinical Testing Completion Memo prior to any statistical analysis of immunogenicity data. Assay results above the LLOQ will be reported, and values below the LLOQ, denoted as BLQ, will be set to $0.5 \times \text{LLOQ}$ for analysis.

CCI

6. ANALYSES AND SUMMARIES

6.1. Primary Endpoints

6.1.1. Primary Safety Endpoints

[figure not shown]
6.1.1.1. Local Reactions

6.1.1.1.1. Main Analysis

- Estimand: The percentage of participants reporting prompted local reactions (redness, swelling, and pain at the injection site) within 10 days after the first vaccination (20vPnC or 13vPnC) ([Section 2.1](#)).
- Analysis set: Safety population ([Section 4](#)).
- Analysis time point: Within 10 days after the first vaccination.

- Analysis methodology: Descriptive statistics. The percentage (%), and the corresponding 95% Clopper-Pearson CI will be presented by vaccine group (20vPnC/saline [Vaccination 1], 13vPnC/PPSV23 [Vaccination 1]). The between-group difference (20vPnC/saline [Vaccination 1] - 13vPnC/PPSV23 [Vaccination 1]) and the corresponding 2-sided 95% CI will be calculated using the Miettinen and Nurminen method¹ ([Section 5.2.1](#)) for each reaction.
- Intercurrent events and missing data: Missing values will not be imputed.
- Reporting results: Count and percentage of participants with the indicated endpoint and the associated 2-sided 95% Clopper-Pearson CI for each and any local reaction in each vaccine group will be presented by maximum severity level. Between-group differences in these percentages and their 2-sided 95% CIs will also be provided.

CCI

6.1.1.2. Prompted Systemic Events

6.1.1.2.1. Main Analysis

- Estimand: The percentage of participants reporting prompted systemic events (fever, headache, fatigue, muscle pain, and joint pain) within 7 days after the first vaccination (20vPnC or 13vPnC) ([Section 2.1](#)).

- Analysis set: Safety population ([Section 4](#)).
- Analysis time point: Within 7 days after vaccination after the first vaccination.
- Analysis methodology: Descriptive statistics. The percentage (%), and the corresponding 95% Clopper-Pearson CI will be presented by vaccine group (20vPnC/saline [Vaccination 1], 13vPnC/PPSV23 [Vaccination 1]). The between-group difference (20vPnC/saline [Vaccination 1] - 13vPnC/PPSV23 [Vaccination 1]) and the corresponding 2-sided 95% CI will be calculated using the Miettinen and Nurminen method¹ ([Section 5.2.1](#)) for each reaction.
- Intercurrent events and missing data: Missing values will not be imputed.
- Reporting results: Count and percentage of participants with the indicated endpoint and the associated 2-sided 95% CI for each and any systemic event in each vaccine group will be presented by maximum severity across severity levels. Between-group differences in these percentages and their 2-sided 95% CIs will also be provided.

CCI

6.1.1.3. Adverse Events

6.1.1.3.1. Main Analysis

- Estimand: The percentage of participants reporting AEs within 1 month after vaccination with 20vPnC or 13vPnC.

- Analysis set: Safety population ([Section 4](#)).
- Analysis time point: Within 1 month after vaccination.
- Analysis methodology: 3-Tiered approach as described in [Section 5.2.1](#).
- Intercurrent events and missing data: No missing values will be imputed except for partial AE start dates ([Section 5.3](#)).
- Reporting results: For all 3 tiers, the numerator (n) and the denominator (N) used in the percentage calculation, the percentage (%), and the corresponding 2-sided 95% Clopper-Pearson CI for participants reporting any AE, by each system organ class and each preferred term within system organ class, will be presented by vaccine group.

In addition, for AEs classified as Tier 2 events, the differences in percentages (20vPnC/saline - 13vPnC/PPSV) and associated 2-sided 95% CIs using the Miettinen and Nurminen method will be provided.

Further, for Tier 1 events, if any are identified, the difference in percentages, the associated 2-sided 95% CI for the risk difference, and the asymptotic p-values will also be provided.

If any nonserious AEs are reported to occur before vaccination at Visit 1, they will not be included in the summary but will be included in the AE listings.

CCI

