### **8.11.2. Visit 2 (Vaccination 2 – 28 to 42 Days After Visit 1)**

Prior to vaccination:

- Ensure and document that the participant continues to be eligible for the study and that none of the temporary delay criteria are met.

- Record nonstudy vaccinations and medications as described in [Section 6.5.3](#).
- Perform a contraception check (see [Section 10.4](#)), if applicable.
- Review the participant's e-diary data and collect the provisioned e-diary (from participants not enrolled **at Japan sites**). Collect stop dates of any e-diary events ongoing on the last day that the e-diary was completed and record stop dates in the CRF.
- Determine if any AEs or SAEs have occurred since Visit 1 and follow up on any previously reported events to determine the outcome (ie, record stop dates or confirm if they are still continuing), record as described in [Section 8.3.1](#), and record concomitant medications used to treat SAEs.
- Measure and record the participant's oral temperature (°C).
- Collect a blood sample of approximately 30 mL for immunogenicity assessments prior to vaccination.
- An **unblinded site staff member** will administer a single 0.5-mL injection of PPSV23 or saline into the deltoid muscle of the nondominant arm.

After vaccination:

- Blinded site staff will observe the participant for 30 minutes after study intervention administration for any reactions. Record any AEs on the CRF and on the Vaccine SAE Reporting Form, as applicable. Record concomitant medications used to treat SAEs.
- For participants enrolled **at Japan sites**:
  - Ask the participant to contact the site staff or investigator immediately during the 10 days after vaccination if the participant experiences redness or swelling at the injection site measuring >20 measuring device units (>10.0 cm) or severe injection site pain (prevents daily activity) to determine if the event requires further assessment by the investigator.
  - Ask the participant to contact site staff or the investigator as soon as possible if the participant experiences any possible Grade 4 prompted local reaction or systemic event (refer to [Section 8.11.4](#)).
  - Remind the participant that he or she may be contacted by site staff to obtain additional information on reports of fever >38.9°C or Grade 3 events entered into the e-diary.

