#### **8.11.3. Visit 3 (Follow-up – 28 to 42 Days After Vaccination 2)**

- Ensure and document that the participant continues to be eligible for the study.
- Record nonstudy vaccinations and concomitant medications as described in [Section 6.5.3](#).
- Perform a contraception check (see [Section 10.4](#)), if applicable.
- Determine if any AEs or SAEs have occurred since Visit 2 and follow up on any previously reported events to determine the outcome (ie, record stop dates or confirm if they are still continuing), record as described in [Section 8.3.1](#), and record concomitant medications used to treat SAEs.
- For participants enrolled **at Japan sites**, review the participant's e-diary data and collect the e-diary. Collect the stop dates of any e-diary events ongoing on the last day that the e-diary was completed and record the stop dates in the CRF.
- Collect a blood sample of approximately 30 mL for immunogenicity assessments.
- The investigator or an authorized designee completes the CRF.

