3.1.1.4. Adverse Events

AEs will be categorized according to MedDRA terms. AEs will be collected from the signing of the ICD through Visit 3 (approximately 1 month after Visit 2). The primary-endpoint AEs within 1 month after vaccination with 20vPnC or 13vPnC will be summarized by system organ class and preferred term on a participant level.

This primary endpoint will be supported by summaries and listings of related AEs, severe AEs, and immediate AEs (within the first 30 minutes after vaccination at Visit 1).

AE reporting will be based on the specific reporting period. Standard algorithms for handling missing AE dates and missing AE severity will be applied as described in the Pfizer vaccine data standard rules.

A 3-tier approach will be used to summarize AEs. Under this approach, AEs are classified into 1 of 3 tiers:

- Tier 1 events: These are prespecified events of clinical importance and are identified in a list in the product's safety review plan. No Tier 1 events have been identified to date for 20vPnC.
- Tier 2 events: These are events that are not Tier 1 but are considered "relatively common." A MedDRA preferred term is defined as a Tier 2 event if there are at least 1% of participants with the AE term in at least 1 vaccine group.
- Tier 3 events: These are events that are neither Tier 1 nor Tier 2.

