5.2. General Methods

Time points for local reactions and systemic events refer to data within 10 and 7 days after vaccination at Visit 1 and Visit 2 (for participants at Japan sites only), respectively.

Prompted local reactions, prompted systemic events, and AEs will be summarized after each vaccination at Visit 1 and Visit 2 by vaccine group.

CIs for all endpoints in the statistical analysis will be presented as 2-sided at the 95% level.

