6.1.1.4. Serious Adverse Events

6.1.1.4.1. Main Analyses

- Estimand: The percentage of participants reporting SAEs within 1 month after vaccination with 20vPnC or 13vPnC.
- Analysis set: Safety population ([Section 4](#)).
- Analysis time point: Within 1 month after vaccination.

- Analysis methodology: Descriptive statistics.
- Intercurrent events and missing data: No missing values will be imputed except for partial SAE start dates (see [Section 5.3](#)).
- Reporting results: The numerator (n) and the denominator (N) used in the percentage calculation, the percentage (%) and the corresponding 95% Clopper-Pearson CI for participants reporting any SAE, by each system organ class and each preferred term within system organ class, will be presented by vaccine group. There will be a listing of all AEs, including SAEs, and a separate listing of SAEs only.

CCI

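### Must the SAP state where the one-month primary AE and SAE period ends, to keep events after PPSV23 out of it?

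*SAP*

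**What the plan says.** The primary safety estimands cover AEs and SAEs in the month after the first vaccine. For SAEs, SAP 6.1.1.4.1 has "The percentage of participants reporting SAEs within 1 month after vaccination with 20vPnC or 13vPnC". For AEs, SAP 6.1.1.3.1 gives the time point as "Analysis time point: Within 1 month after vaccination". The start of the period is fixed in the same section: "If any nonserious AEs are reported to occur before vaccination at Visit 1, they will not be included in the summary". No matching end is visible.

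Other passages bear on the end:

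- SAP 3.1.1.4: "AE reporting will be based on the specific reporting period". It also refers missing AE dates to the sponsor's vaccine data standard rules.
- SAP 5.2: "AEs will be summarized after each vaccination at Visit 1 and Visit 2 by vaccine group".
- Protocol 8.11.2, among the steps before the second injection: "Determine if any AEs or SAEs have occurred since Visit 1".
- Protocol 8.11.3, at the last visit: "Determine if any AEs or SAEs have occurred since Visit 2".
- SAP 3.1.2 places Visit 2 about one month after Visit 1, SAP 3.1.1.4 places Visit 3 about one month after Visit 2, and Protocol 8.1.1 equates one month with 28 to 42 days for the sera.

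A partial AE start date "will be imputed by assigning the earliest possible start date using all available information". The rest of that sentence in SAP 5.3 names the AE stop date and the participant's vaccination dates as part of that information.

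**The concern.** Elsewhere the SAP is numerically exact: Days 1 to 10 for local reactions, Days 1 to 7 for systemic events, and 27 to 49 days for evaluable sera. The AE and SAE period is the one primary endpoint period without numeric limits in the visible text. AE collection runs on through Visit 3, so it does not impose a cut-off either.

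A programmer could take one month literally as 30 or 31 days. Controls given PPSV23 early in the visit window would then have their first days after PPSV23 counted as following 13vPnC, while the same days in the other group follow saline. That would tend to raise the control percentage and flatter 20vPnC in the between-group differences for Tier 2 events. The same events would appear again in the summary after Vaccination 2. For participants vaccinated late in the window, the days between the fixed end and Vaccination 2 would belong to neither summary.

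**Working it through.** The documents state no figure for this point, so there is none to reproduce. The check has two parts: which reading the text supports, and how large the effect would be under the other one.

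**Which reading.** The estimands name 20vPnC and 13vPnC, not PPSV23. AEs since Visit 1 are asked about before the second injection, AEs since Visit 2 are asked about at Visit 3, and the SAP summarizes AEs after each of the two vaccinations. One month is the documents' own label for the interval between visits. Together these give two adjoining periods that meet at Vaccination 2. No visible passage mentions a 28-, 30- or 31-day AE window.

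**Size under a fixed window.** Inputs:

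- Vaccination 2 at d = 28 to 42 days after Vaccination 1 (Protocol 1.3), so 15 permitted values.
- The day of vaccination is Day 1 (Protocol 8.11, SAP 3.4), so Vaccination 2 falls on Day d + 1.
- 700 participants per group (Protocol 9.2).
- Assumption: d is spread evenly over the 15 values. The documents give no visit-day distribution.

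For a period whose last day is Day N, counting the day of Vaccination 2 as overlap:

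- overlap days = max(0, N − d)
- days in neither period = max(0, d − N)

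| Last day | Controls with overlap | Of 700 | Most overlap days | Participants with days in neither period | Mean such days |
|---|---|---|---|---|---|
| Vaccination 2 | 0 | 0 | 0 | 0 | 0 |
| Day 28 | 0/15 = 0% | 0 | 0 | 14/15 = 93% | 105/15 = 7.0 |
| Day 30 | 2/15 = 13% | 93 | 2 | 12/15 = 80% | 78/15 = 5.2 |
| Day 31 | 3/15 = 20% | 140 | 3 | 11/15 = 73% | 66/15 = 4.4 |

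Counting elapsed days instead of numbered days (an end 30 or 31 days after Vaccination 1) gives 3/15 = 20% (140 controls) and 4/15 = 27% (187 controls).

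To turn overlap into an effect, suppose that 2% to 10% of the overlapping controls first report an AE in those days. This range is an assumption; the documents give no such rate. The control percentage would then rise by between 13.3% × 2% = 0.3 points (Day 30 end) and 20% × 10% = 2.0 points (Day 31 end).

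**Partial dates.** SAP 5.3 already uses the vaccination dates to produce an imputed start date. That date then falls in one period or the other like any recorded date. Only a date that lands on the day of Vaccination 2 stays open, which is the same-day case and not a further gap.

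**The case for a change.** The strongest case for a change is that the visible text does not settle the boundary, and that accepting a split at Vaccination 2 still leaves some cases unassigned. The AE questioning, the injection and the 30-minute observation all take place at Visit 2, so the calendar date alone does not place an event starting that day. Participants who stay in the study without Vaccination 2 have no second injection to close the period, and Protocol 7.1 again says only one month for their follow-up. A sentence or two would settle this.

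These points are true of the visible text, but they carry little weight. A participant who never receives PPSV23 has no PPSV23 events to misplace. The same-day case concerns a single day. Assigning it by clock time would need AE onset times: Protocol 6.4 records dose times, and SAP 3.1.1.4 plans a summary of immediate AEs after Visit 1, but no visible passage says that onset time is collected for AEs in general. The sponsor's data standard rules and the redacted blocks after the two main analyses may already define the period or the same-day rule, and their absence here is not an omission from the plan. What stands is an optional clarification that a programming specification can carry.

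**Conclusion.** No change to the plan follows. The end of the period is not written in the visible text, but the visit structure and the summaries after each vaccination imply that it ends at Vaccination 2. On that reading no events after PPSV23 enter the first period and no days are lost. The 13% and 20% overlap figures apply only to a fixed window that the documents nowhere adopt, and they rest on evenly spread visits.

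Even under such a window, the effect would be confined to descriptive AE and SAE percentages and the Tier 2 differences. Prompted reactions have their own day limits, and the immunogenicity analyses and noninferiority tests do not use AE periods. No bias has been shown. Writing the end down would only record the split that the plan already implies.

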6.1.1.4. Serious Adverse Events

6.1.1.4.1. Main Analyses

- Estimand: The percentage of participants reporting SAEs within 1 month after vaccination with 20vPnC or 13vPnC.
- Analysis set: Safety population ([Section 4](#)).
- Analysis time point: Within 1 month after vaccination.

- Analysis methodology: Descriptive statistics.
- Intercurrent events and missing data: No missing values will be imputed except for partial SAE start dates (see [Section 5.3](#)).
- Reporting results: The numerator (n) and the denominator (N) used in the percentage calculation, the percentage (%) and the corresponding 95% Clopper-Pearson CI for participants reporting any SAE, by each system organ class and each preferred term within system organ class, will be presented by vaccine group. There will be a listing of all AEs, including SAEs, and a separate listing of SAEs only.

CCI

6.1.2. Primary Immunogenicity Endpoint

The ordering of the pneumococcal serotypes in summaries will be as follows:

- 13vPnC serotypes: 1, 3, 4, 5, 6A, 6B, 7F, 9V, 14, 18C, 19A, 19F, 23F; and
- Additional 7 serotypes: 8, 10A, 11A, 12F, 15B, 22F, 33F.

6.1.2.1. Main Analysis

- Estimand:
 - For each of the 13 serotypes: GMR of serotype-specific OPA titers 1 month after 20vPnC to the serotype-specific OPA titers 1 month after 13vPnC.
 - For each of the 7 additional serotypes: GMR of serotype-specific OPA titers 1 month after 20vPnC to the serotype-specific OPA titers 1 month after PPSV23.
- Analysis set: Evaluable 13-matched immunogenicity (13vPnC serotypes), evaluable 7-additional immunogenicity population (7 additional serotypes), CCI
- Analysis time point: 1 Month after administration of 20vPnC (Visit 2), 1 month after administration of 13vPnC (Visit 2), or 1 month after administration of PPSV23 (Visit 3).
- Analysis methodology: Linear regression model with terms for corresponding baseline OPA titer, age, sex (male or female), country (Japan, Korea, or Taiwan), smoking status (current smoker, ex-smoker, or never smoked), and vaccine group (20vPnC/saline group or 13vPnC/PPSV23 group).

- Reporting results: The LS GMTs and associated 95% CIs for serotype-specific OPA titers from each vaccine group, as well as the model-based OPA GMRs with their associated 95% CIs, will be summarized separately for the 13 matching pneumococcal serotypes and for the 7 additional serotypes.

If participants' racial designation is different from their enrollment country, the factor for linear regression is based on the enrollment country.

Reporting results:

The LS GMTs and associated 95% CIs for serotype-specific OPA titers from each vaccine group, as well as the model-based OPA GMRs with their associated 95% CIs, will be summarized separately for the 13 matching pneumococcal serotypes and for the 7 additional serotypes.

Figures:

A forest plot of GMRs with 95% CIs for all 20 serotypes, with a vertical reference line corresponding to GMR=0.5, will be presented.

- CCI

[REDACTED]

[REDACTED]

6.2. Secondary Endpoints

6.2.1. Secondary Safety Endpoints (For Participants Enrolled at Japan Site Only)

6.2.1.1. Local Reactions

6.2.1.1.1. Main Analysis

- Estimand: The percentage of participants reporting prompted local reactions (redness, swelling, and pain at the injection site) within 10 days after the second vaccination (PPSV23 or saline) (Section 2.1).
- Analysis set: Vaccinated participants receiving PPPSV23 in the 13vPnC/PPSV23 group or saline in the 20vPnC/saline group in the safety population (Section 4).
- Analysis time point: Within 10 days after vaccination with PPPSV23 in the 13vPnC/PPSV23 group or saline in the 20vPnC/saline group.
- Analysis methodology: The percentage (%) and the corresponding 95% Clopper-Pearson CI will be presented.
- Intercurrent events and missing data: Missing values will not be imputed.
- Reporting results: Count and percentage of participants with the indicated endpoint and the associated 2-sided 95% CI for each and any local reaction after each dose in each vaccine group will be presented by maximum severity across severity levels.

[figure not shown]
CCI

[REDACTED]

[REDACTED]

[REDACTED]

CCI

6.2.1.2. Systemic Events

- Estimand: The percentage of participants reporting prompted systemic events (fever, headache, fatigue, muscle pain, and joint pain) within 7 days after the second vaccination (PPSV23 or saline) (Section 2.1).
- Analysis set: Vaccinated participants receiving PPPSV23 in the 13vPnC/PPSV23 group or saline in the 20vPnC/saline group in the safety population (Section 4).
- Analysis time point: Within 7 days after vaccination with PPSV23 in the 13vPnC/PPSV23 group or saline in the 20vPnC/saline group.
- Analysis methodology: The percentage (%) and the corresponding 95% Clopper-Pearson CI will be presented by vaccine group.
- Intercurrent events and missing data: Missing values will not be imputed.
- Reporting results: Count and percentage of participants with the indicated endpoint and the associated 2-sided 95% CI for each and any local reaction after each dose in each vaccine group will be presented by maximum severity across severity levels.

CCI

[figure not shown]

CCI

6.2.2. Secondary Immunogenicity Endpoints

[figure not shown]
6.2.2.1. Main Analysis

- Estimand: Serotype-specific OPA GMTs 1 month after vaccination in each vaccine group.
- Analysis set: Evaluable 13-matched immunogenicity (13vPnC serotypes), evaluable 7-additional immunogenicity population (7 additional serotypes), CCI

- Analysis time point: 1 month after administration of 20vPnC (Visit 2), 1 month after administration of 13vPnC (Visit 2), or 1 month after administration of PPSV23 (Visit 3).
- Analysis methodology: OPA GMTs and the 2-sided 95% CIs for each vaccine group based on the Student's t-distribution (Section 5.2.2.1).
- Reporting results: Observed GMTs and 95% CIs for serotype-specific OPA titers will be presented for each vaccine group, both before vaccination and 1 month after vaccination.

Figures:

Bar charts for observed OPA GMTs and corresponding 95% CIs for the 13 serotypes will be plotted at before Vaccination 1 and 1 month after Vaccination 1 for each vaccine group. Similar plots will be generated for before Vaccination 1 and 1 month after vaccination (Vaccination 1 for the 20vPnC/saline group and Vaccination 2 for the 13vPnC/PPSV23 group) for the 7 additional serotypes.

